6. DEFINITIONS AND DESCRIPTIONS OF ASSESSMENTS AND ENDPOINTS

6.1 Pharmacokinetic/Pharmacodynamic Endpoints and Assessments

No pharmacokinetic/pharmacodynamic endpoints or assessments will be performed in this study.

6.2 Efficacy Variables

6.2.1 Primary Efficacy Variable

- The primary efficacy variable is the assessment of pain by the NRS after the administration of intranasal ketorlac (sprix).

6.2.2 Secondary Efficacy Variables

The secondary efficacy variables are the global pain assessment scores, the global assessment of analgesia (pain relief) scores, the patient questionnaire and the health care provider questionnaire which are completed before the patient leaves the clinical site (e.g. ED).

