5.1.4.2 Study Pain Assessments

Study pain assessments will be done before and after the administration of the single dose of intranasal ketorolac (sprix). All patients will have a minimum of two pain scores (NRS): a baseline (pre administration of the intranasal ketorolac) and a post administration of intranasal ketorolac. The time that the pain score is done, whether at baseline or post intranasal administration of the ketorolac, will be recorded any time a baseline or post-treatment NRS pain score is done. A post-treatment NRS pain score will be done immediately prior to the patient leaving the ED and immediately prior to the patient receiving rescue medication (e.g. any additional pain medication or sedatives) with the time post-treatment to be recorded. Depending on the length of time the patient is in the ED, additional NRS pain scores will be done, if possible. While the patient is in the ED, additional NRS pain scores will be recorded at specified times after study drug administration; specifically, at 20 minutes, 40 minutes, 1 hour, 2 hours, 3 hours, 4 hours, 5 hours and 6 hours for as long as the patient remains in the clinical site, in addition to time 0 (baseline = before administration of the study drug). (See Appendix 1) The pain scores will be compared and analyzed for statistical significance comparing the baseline (pre-study drug administration) with the "post-study drug administration or "treatment" pain scores.

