5.1.4.3 Study Questionnaires

Study Questionnaires will be done by the patient and the health care provider after administration of the study drug (intranasal ketorolac [sprix]), prior to the patient leaving the clinical site. (See Appendix 2)

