5.1.4.4. Standard-of-Care Procedures: Pain Management

Patients may receive additional medications as part of their emergency department treatment including additional pain medications, such as opioids. Any additional medications administered will be recorded. The need for additional medications (including the drug administered, the dose, the time, and the route of administration) will

be recorded. The need for additional pain medications (or the lack of need for additional pain medications) may also be a secondary efficacy endpoint.

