5.1.6 Efficacy Assessments

5.1.6.1 Pain Assessments

Pain scores will be recorded and documented before administration of the intranasal ketorolac (sprix) for a baseline pain assessment and at specified intervals after the administration of intranasal ketorolac (sprix). Post-treatment pain scores will be recorded immediately prior to discharge from the ED and immediately prior to any rescue (e.g. pain or sedative) medication. Post treatment pain scores will be collected for as long as the patient is in the clinical site and will be at 20 minutes, 40 minutes, 1 hour and for 1 hour intervals post treatment up to 6 hours (e.g. at 1, 2, 3, 4, 5, and 6 hours) in addition to pain scores immediately prior to rescue medication and immediately prior to discharge from the ED. Pain assessments will be by the Numeric Rating Scale (NRS).where 0 = no pain and 100 = the worst pain imaginable. (See Appendix 1)

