5.1.6.2. Patient Questionnaires

Patient questionnaires will be obtained after administration of the intranasal ketorolac (sprix) and prior to the patient leaving the clinical site. (See Appendix 2)

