Appendix 1B: Global Pain Assessment Scale

How would you rate your pain?

0 = none 1 = a little (mild) 2 = some (moderate) 3 = severe
4 = very severe (extreme)

**Appendix 1C: Global Assessment of Analgesia
(Global Assessment of Pain Relief)**

How would you rate your pain relief?

0 = poor 1 = fair 2 = good 3 = very good 4 = excellent

**Appendix 1D: Calculated Pain Assessments:
Pain Intensity Difference (PID)
Summed Pain Intensity Difference (SPID)
(Weighted Sum of PID)
Total Pain Assessment Relief (TOTPAR)
(Weighted sum of pain relief scores)**

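### No pre-rescue rating or completion time is required for the global scales and questionnaires, so in rescued patients they may reflect ketorolac plus rescue

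*Combined protocol and SAP*

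**What the plan says.** Section 5.1.4.4 permits rescue: "Patients may receive additional medications as part of their emergency department treatment including additional pain medications, such as opioids". The drug, dose, route and time are recorded.

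For the NRS, section 5.1.4.2 requires a score "immediately prior to the patient receiving rescue medication (e.g. any additional pain medication or sedatives", with its time noted. Section 5.1.6.1 repeats the rule, "Post-treatment pain scores will be recorded immediately prior to discharge from the ED and immediately prior to any rescue (e.g. pain or sedative) medication", and names one instrument for it: "Pain assessments will be by the Numeric Rating Scale (NRS".

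For the other four instruments the timing is looser:

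- Section 5.1.4.3, both questionnaires: "Study Questionnaires will be done by the patient and the health care provider after administration of the study drug", and before the patient leaves.
- Section 5.1.6.2: "Patient questionnaires will be obtained after administration of the intranasal ketorolac (sprix) and prior to the patient leaving the clinical site". Section 5.1.6.3 sets the same window for the provider form.
- Section 6.2.2 lists the two global scales and both questionnaires as secondary efficacy variables, "which are completed before the patient leaves the clinical site (e.g. ED".

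None of these sections mentions rescue or asks for the time at which a form is completed. Section 7.2 names tests for the pain scales and questionnaires but does not say how a rating made after rescue is treated.

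**The concern.** The protocol recognises that a pain score taken after an opioid no longer describes ketorolac alone, and it protects the NRS against this. The same protection is not extended to the other patient- and provider-reported efficacy measures.

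The relief item in Appendix 1C, "How would you rate your pain relief", names no drug. A patient whom ketorolac did not help, and who was then relieved by an opioid, could truthfully give a high rating. The patient questionnaire and the provider's treatment-success item do name the intranasal product. Even so, they ask the respondent to separate two analgesics from memory. The trial is nonblinded and has no control group, so no comparison would expose the mixture.

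For the pain and relief items the direction is predictable: rescue that works makes ketorolac look better. Both global scales are efficacy outcomes wherever one looks. Section 2.2.1 places them among the primary variables and section 6.2.2 among the secondary ones. That disagreement is a separate matter.

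**Working it through.** **The plan's own figure.** Section 7.1 gives 25 patients for 80% power at an effect size of 0.56 (mean PID divided by its SD). Taking 0.05 as two-sided, the normal approximation gives n = ((1.960 + 0.842)/0.56)² = 25.03, and power of 0.7996 at n = 25. The figure reproduces on that basis. It concerns the NRS-based PID, so it neither supports nor weakens this point.

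**The rules side by side.**

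| | NRS | Two global scales | Two questionnaires |
|---|---|---|---|
| Score required just before rescue | Yes (5.1.4.2, 5.1.6.1) | Not stated | Not stated |
| Latest time | Just before leaving | Before leaving (6.2.2) | Before leaving (5.1.4.3, 5.1.6.2, 5.1.6.3) |
| Time of rating recorded | Yes (5.1.4.2) | Not stated | Not stated |
| Analysis rule after rescue | None in 7.2 | None in 7.2 | None in 7.2 |

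A site that completes the forms before rescue complies with the text. So does a site that completes them after rescue. The time of rescue is known, but without a time on the form the analyst may be unable to tell which case applies.

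**Possible size.** The documents give no ED rescue rate, so the rescued share r is an assumption, taken here as 10% to 50%.

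- Patients rescued before rating = 25 × r.
- Largest possible shift in a yes/no proportion = r. This is reached only if every such patient would have answered no before rescue and answers yes afterwards.
- Shift if half of them change their answer = 0.5 × r.
- Shift in the mean of a 0–4 scale = r × 1 if rescue moves each such rating by one point.

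| Assumed r | Patients of 25 | Largest shift, yes/no | Shift if half change | Mean shift, one point each |
|---|---|---|---|---|
| 10% | 2.5 | 10 points | 5 points | 0.1 |
| 20% | 5 | 20 points | 10 points | 0.2 |
| 30% | 7.5 | 30 points | 15 points | 0.3 |
| 40% | 10 | 40 points | 20 points | 0.4 |
| 50% | 12.5 | 50 points | 25 points | 0.5 |

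The largest-shift column is a ceiling, not an estimate. The last two columns each need a further assumption that the documents cannot supply.

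**The case against.** A reader might infer that these forms are always completed after rescue, that no pre-rescue rating will exist, and that nothing can be done later. The documents do not support any of the three.

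- **Order.** The text sets a window. Completion after the spray and before rescue falls inside it.
- **Repeated ratings.** Section 2.2.1 compares the global scales with baseline, section 4.2 calls for all baseline pain assessments before dosing, and Appendix 1D lists TOTPAR, a weighted sum of relief scores, which implies relief ratings at more than one time. In section 6.2.2 the clause about completion before leaving may apply only to the questionnaires. Section 5 also refers to Figure 1, which is not reproduced in the text reviewed. These point to more than one global rating, but no readable section schedules one before rescue.
- **Analysis.** Rescue drugs and times are recorded (4.6, 5.1.4.4 and the medications section of 5.1.5), so rescued patients can be identified and then reported separately or counted as non-responders. It does not follow that they must be recorded as ketorolac successes. However, section 7.2 plans no such handling, and it would not recover a rating that was never taken.

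Two further objections carry weight. Several questionnaire items concern satisfaction, side effects or future use of the spray and are not direct measures of pain. Section 6.2.1 names the NRS alone as primary, and the sample size rests on NRS-based PID, so the main outcome keeps its pre-rescue score. These limit the importance of the point but do not close the gap.

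**Conclusion.** The point holds as a gap in specification. The readable text requires no pre-rescue rating and no completion time for the two global scales or the two questionnaires, and section 7.2 has no rule for post-rescue ratings. A site following the protocol exactly could therefore rate ketorolac plus rescue on efficacy variables.

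The bias would favour ketorolac, provided that rescue relieves pain and that some rescued patients are rated afterwards. Its size cannot be estimated from the documents. With 10% to 50% rescued before rating, the ceiling on a yes/no proportion is 10 to 50 percentage points. The matter should be put right, but it does not undermine the NRS outcome, for which a pre-rescue score is already required.

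**What to change.** In sections 5.1.4.3, 5.1.6.2, 5.1.6.3 and 6.2.2, state that the two global items are completed together with the pre-rescue NRS already required, with the questionnaires following if time allows. If there is no rescue, all four are completed before departure. The forms must not delay rescue; the change concerns only when ratings are collected. Add a completion time for each form to the case report form.

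In section 7.2, state that:

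- the pre-rescue rating is the one analysed for rescued patients;
- any departure rating made after rescue is descriptive only;
- rescued patients with no pre-rescue rating are either reported separately or counted as non-responders. Choose one in advance and, if the latter, define response for each instrument.

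If Figure 1 already schedules repeated global ratings, the text should be brought into line with it.

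The cost is a wording change, a time field, and about a minute when an NRS is already being taken. No extra patients or staff are needed. There are downsides. Rating times will vary between patients. Some ratings may come early after dosing: the dental-surgery trial summarised in section 1.2 reports 66.0 minutes to meaningful relief with ketorolac. Some rescued patients may complete only the two global items. Recorded times at least make this variation visible.

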6.3 Safety Variables

6.3.1 Primary Safety Variable

The primary safety variables are the occurrence of adverse events (after the intranasal ketorolac has been administered).

6.3.2 Secondary Safety Variables

The secondary safety variables are the vital signs taken after the intranasal ketorolac has been administered. An additional secondary safety variable is the appearance of the nasal mucosa after the administration of the intranasal ketorolac and prior to the patient leaving the clinical site. The nasal mucosa (both sides) will be examined for any abnormalities such as erythema, discoloration, swelling, etc at baseline (prior to administration of the intranasal study drug, sprix), and after administration of the intranasal study drug, sprix).

6.3.3 Adverse Events

6.3.3.1 Definitions

An adverse event is defined as any untoward medical occurrence in a subject administered a study treatment and which did not necessarily have a causal relationship with the treatment. An adverse event could therefore, be any unfavorable and unintended sign, symptom, or disease temporally associated with the use of a study treatment, whether or not related to the study treatment.

For the purposes of this study, a treatment-emergent adverse event is defined as any adverse event that occurs during the emergency department visit and after administration of the intranasal ketorolac (sprix). The treating clinician should reflect whether the event was considered to be “possibly related” or “not related” to any protocol mandated procedures during the study.

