5.1.4 Study Treatment

Study treatment assessments will be performed during the time the patient is in the clinical site and will be performed, if indicated at specific times (see subsections below) The following information will be obtained and the findings will be recorded:

Study treatment assessments at specified times (baseline prior to administration and after administration of intranasal ketorolac [sprix]) including vital signs (baseline, before administration of intranasal ketorolac) and after administration of intranasal ketorolac (prior to the patient leaving the clinical site, e.g. emergency department).

- Pain assessments
- Patient/health care provider questionnaires will be done prior to the patient leaving the clinical site
- Any side effects/adverse events
- Vital signs

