5.1.6.6 Side Effects/Adverse Events

Any and all side effects/adverse effects will be documented on the case report form. The health care provider will determine whether the side effect/adverse event is or is not related to the intranasal ketorolac (sprix).

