7.3 Safety

- Safety will be assessed by adverse events documented on the case report form.
- Safety will be assessed by clinical assessment including vital signs before and after administration of the study drug, intranasal ketorolac (sprix).
- Safety will also be assessed by clinical assessment of the nasal mucosa before and after administration of the study drug, intranasal ketorolac (sprix).

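### The safety analysis plans no separation of adverse events and vital signs before and after rescue medication

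*Combined protocol and SAP*

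**What the plan says.** Adverse events are the primary safety variable: "The primary safety variables are the occurrence of adverse events (after the intranasal ketorolac has been administered") (6.3.1, and likewise 2.2.3.1). Section 6.3.3.1 defines a treatment-emergent event as "any adverse event that occurs during the emergency department visit and after administration of the intranasal ketorolac (sprix"). The window has no cut at rescue.

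Vital signs are secondary: "The secondary safety variables are the vital signs taken after the intranasal ketorolac has been administered" (6.3.2). Section 5.1.4 fixes the post-dose set only as "after administration of intranasal ketorolac (prior to the patient leaving the clinical site, e.g. emergency department").

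On other drugs, 5.1.4.4 states: "Patients may receive additional medications as part of their emergency department treatment including additional pain medications, such as opioids". Section 5.1.4.2 takes rescue to include any further analgesic or sedative. The drug, dose, route and time of each are recorded (4.6, 5.1.4.4, 5.1.5.3 on medications).

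On cause, 5.1.6.6 states: "The health care provider will determine whether the side effect/adverse event is or is not related to the intranasal ketorolac (sprix"). Section 6.3.3.1 instead asks whether an event is possibly related, or not related, to procedures that the protocol mandates.

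On analysis, 7.3 lists the adverse events documented on the case report form and the nasal examination, and for vital signs says: "Safety will be assessed by clinical assessment including vital signs before and after administration of the study drug". It does not mention rescue or relatedness.

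**The concern.** The protocol guards its pain measurement against rescue but not its safety measurements. An NRS score is required immediately before any rescue drug (5.1.4.2, 5.1.6.1). No vital signs are required at that contact, although study staff are already collecting data then.

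This matters for this drug in particular. Section 1.1 argues that ketorolac does not cause respiratory depression or hypotension, and 1.3 claims a lower incidence of both than with opioids. Both would show in vital signs. If the only post-dose reading follows a rescue opioid, an effect of the kind that ketorolac is said to avoid could appear as a change from before to after ketorolac.

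The studies summarised in 1.2 show why a comparator matters. In the three where patients had morphine by patient-controlled analgesia, 93% to 100% of patients in every arm had an adverse event, placebo included. Surgery contributed to that background, but the placebo arm carried it too. Here there is one arm, so a rescue contribution cannot be subtracted. At stake is how clearly the secondary objective, safety and tolerability (2.1.2), can be read in rescued patients.

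**Working it through.** **The plan's own figure.** Section 7 states no safety figure. Its one calculated figure is efficacy power, which reproduces under a two-sided normal approximation: n = ((1.960 + 0.842)/0.56)² = 25.03, and power at 25 = Φ(0.56 × 5 − 1.960) = 0.7996. It does not bear on this point.

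**The provisions side by side.**

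| Measure | Required immediately before rescue? | Time required? | Relatedness judged? |
|---|---|---|---|
| NRS pain score | Yes (5.1.4.2, 5.1.6.1) | Yes (5.1.4.2) | Not applicable |
| Vital signs | No (5.1.4) | Not stated | No |
| Adverse events | No checkpoint | Onset time not stated | Yes, in two wordings (5.1.6.6, 6.3.3.1) |
| Rescue drug | Not applicable | Yes (5.1.4.4, 5.1.5.3) | Not applicable |

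**What follows for each kind of patient.**

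1. No rescue: all post-dose events and vital signs are free of rescue effects.
2. Rescued, with post-dose vital signs taken before rescue: the reading is also free of them, but no stated time stamp would show this to the analyst.
3. Rescued, with post-dose vital signs taken only afterwards: the change combines ketorolac, rescue and the course of the illness. Nothing in 7.3 separates them, and no causality judgement applies to vital-sign values.
4. Adverse events in rescued patients: the provider's judgement can mark an event due to rescue as not related, but 7.3 does not use it. Rescue time alone cannot place an event before or after rescue; onset time is needed too.

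**Illustration of size.** The documents give neither a rescue rate nor an event rate on rescue drugs, so every rate below is an assumption.

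- Vital signs: if 20% to 60% are rescued, 25 × 0.20 = 5 to 25 × 0.60 = 15 patients could have a post-dose reading that follows rescue. These are upper bounds, because some readings may come first.
- Adverse events: let a be the risk of an event without rescue, o the added independent risk from rescue, and r the proportion rescued. Expected patients with an event = 25 × [1 − (1 − a)(1 − r·o)]. Take a = 0.10 and o = 0.20:

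| r | Expected patients with an event | Excess over r = 0 |
|---|---|---|
| 0 | 2.50 | – |
| 0.10 | 25 × (1 − 0.90 × 0.98) = 2.95 | 0.45 |
| 0.25 | 25 × (1 − 0.90 × 0.95) = 3.63 | 1.13 |
| 0.50 | 25 × (1 − 0.90 × 0.90) = 4.75 | 2.25 |
| 0.75 | 25 × (1 − 0.90 × 0.85) = 5.88 | 3.38 |

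With o = 0.40 and r = 0.75 the figure is 25 × (1 − 0.90 × 0.70) = 9.25. The range is wide, and the documents do not narrow it.

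**The case against.** The strongest reply is that the adverse event plan is conventional. Counting every post-dose event and then judging cause is normal practice, and any resulting bias overstates harm, the cautious direction for a safety result. Both relatedness wordings let an event due to rescue be called not related, because 5.1.4.4 treats rescue as standard of care that patients may receive, not as something the protocol mandates. Rescue times are recorded. The case report form is not among the documents and may already have a field for onset time. Safety is a secondary, descriptive objective with no test or power at stake.

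Most of this stands. A reader might infer that opioid effects are simply booked as ketorolac harm, or that rescued patients yield no ketorolac-specific safety reading. The documents do not support either. The relatedness judgement gives a partial separation of events. The nasal mucosa is examined before and after dosing (5.1.4.1, 5.1.6.5, 6.3.2), and the questionnaires ask about satisfaction with the spray (Appendix 2A) and unacceptable side effects from it (Appendix 2B). These inform safety and tolerability in rescued patients as well. Nor does 5.1.4 place vital signs at departure: mixing arises only when the reading follows rescue.

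What the reply leaves unanswered is narrower. Section 7.3 uses neither relatedness nor rescue time, the relatedness judgement is made unblinded (3.1) against two different referents, and vital-sign values have no safeguard.

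**Conclusion.** The concern holds as a gap in data collection and analysis: no separation at rescue is planned for adverse events or vital signs. It is firmest for vital signs. Where the first post-dose set follows rescue, a single-arm comparison cannot attribute the change to ketorolac. For adverse events the gap is a missing tabulation and, as far as the documents show, a missing onset time; the count of all post-dose events is sound and should stay.

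The size is unknown. The figures of up to 5 to 15 patients for vital signs, and roughly 0.5 to 3.4 extra patients with an event (6.75 in the most extreme case computed), rest wholly on assumed rates. Sample size, power and the efficacy analysis are unaffected. A reader might conclude that the trial cannot meet its safety objective in rescued patients; the measures tied to the spray and the relatedness judgement show that this goes too far. The change is still worth making before enrolment, because times and readings not taken at the bedside may not be recoverable later.

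**What to change.** 1. **Vital signs.** In 5.1.4, add a timed set at the NRS contact already required immediately before rescue, and keep the pre-departure set, also timed. In 7.3, use the pre-rescue set (or the pre-departure set if there is no rescue) for the main before/after comparison, and show the departure set alongside.
2. **Adverse events.** Record onset time. In 7.3, report all treatment-emergent events, split by onset before and after first rescue and by relatedness. Do not replace the total with the pre-rescue count: that would drop later-onset ketorolac effects and shorten follow-up in the patients who needed rescue.
3. **Relatedness.** Use one question with one response scale in 5.1.6.6 and 6.3.3.1, with intranasal ketorolac as the referent.

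The cost is one extra set of vital signs in rescued patients, one time field for event onset if the form lacks it, a time on each vital-sign set, and edits to four sections. The pre-rescue figures will rest on shorter follow-up, so they should be shown with their observation time. The fix does not supply a control: pre-rescue changes will still include the course of the presenting illness.
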